7.5 Follow-up for Adverse Events

All subjects will be interviewed about their recent history of psychiatric and medical illnesses, psychosocial stressors, current medications and health status. In addition, vital signs including pulse rate, systolic blood pressure, and body weight will be obtained at each visit. The UKU Side Effect Rating Scale,¹³⁷ a comprehensive rating scale for monitoring adverse events (AE) in clinical trials, will also be completed at all follow-up visits.

7.6 Safety Monitoring

We will arrange for **Data Safety Monitoring Committee** meetings at approximately six month intervals. The DSMC will consist of one external and one internal member, [name], an expert geriatric psychiatrist, [name] a geriatrician, and a statistician- methodologist [name]. Both DSMC members have considerable experience in geriatric clinical issues. The DSMC will meet at least once every six months to review study progress. Members of the committee agree to keep all information confidential. Those members of the investigative group that are involved with the treatment and assessment of patients within the study will not review data that involve the comparison of outcomes (i.e., adverse events, treatment response, remission, etc.).

The Board will also issue a report annually to the PI and the IRB. The board will review summaries of the study progress to ensure that consent documentation is properly obtained and stored. They will also review progress in filling subject recruitment ethnic requirements. They will also determine whether study coordinators and investigators are collecting and organizing data properly. Key personnel will provide progress reports to facilitate this review. The board will also review any recent research relevant to the study. The summary reports will provide data on enrollment and adverse events. Additional support for these activities will be provided by the CTSI of the UCLA School of Medicine, which appointed Associate Dean, [name], and a full-time staff member, [name]., to assist in data safety monitoring in all protocols administered through the CTSI. A committee consisting of at least four medical school faculty

members will review the findings of the DSMC and make recommendations for additional action as needed.

8. INTERVENTION DISCONTINUATION

Subjects have the right to refuse to participate or to withdraw from the research study and discontinue participation at any time. Subjects will continue to be followed with their permission if study intervention is discontinued.

All subjects will be medically stable prior to entry into the study protocol and will be stable on psychotropic medications or ongoing psychotherapy for at least 4 months. However, if subjects engage in alternate treatments, they will be advised to inform the PI at every visit. If the alternate treatment is judged to interfere significantly with the intervention, the subject will be withdrawn from the interventions but followed naturally for 12 months. Subjects will be informed about an option of pursuing clinical care in the community.

Subjects who do not improve or get worse during acute intervention phase or relapse during the continuation phase will be offered treatment outside the protocol in the Geriatric Psychiatry Clinics, or other community clinics. They will also be invited to come for the 6 and 12 month follow-up to determine their progress and the patterns of response to treatment while controlling for any changes in treatment.

9. STATISTICAL CONSIDERATIONS

Statistical Analysis Plan. To clarify, for our primary analysis of assessing treatment effects, the GLMM model proposed will not include treatment adherence or time in practice. Once treatment effects are interpreted from our primary analysis, as a secondary analysis we will include these variables (i.e., treatment adherence or time in practice) as well as their interactions with treatment into the model, to assess whether the confirmed treatment effects depend on (or vary as a function of) time in practice. In addition this dependence is allowed to vary between treatment groups. This is equivalent to correlating a continuous time in practice measure with the treatment effects within each group. Hence, this secondary analysis will lead to a separate interpretation than our primary analysis assessing treatment effects.

9.1 General Design Issues

We have tested all of the procedures in the pilot study, and are hopeful that the majority of participants will be able to tolerate the duration and complexity of the tests. All estimates of dropouts are based on our pilot experiences in several studies. If we find our estimates of adherence being different, we will factor those in the analyses. Other potential pitfalls are discussed in the Human Subject section.

9.2 Sample Size and Randomization

Power and sample size estimate: We assume that dropout will be at 10% and 20% at the end of 12 week treatment phase and 6 and 12 month follow-up, respectively. For Aim 1, if the treatment main effects are linear over the 12 week treatment phase on HAMD, our design with 7 time points (baseline, 2, 4, 6, 8, 10, 12 weeks) and with complete data on 99 subjects within each arm (10% dropout) will have 80% power at significance level $\alpha=0.05$ for detecting a treatment and time interaction corresponding to no difference at baseline and a difference of $d = 0.32$ SDs between any two arm at the end follow-up. Our R21 project found an effect size of 0.65 in HAMD between TCC and HEW at 12 weeks. If treatment effects continue to grow linearly over the 6 and

12 month follow-up, our design with complete data on 88 subjects within each arm (20% dropout) will have 80% power at significance level $\alpha=0.05$ for detecting a group difference between any two arms of $d = 0.36$ SDs at 6 and 12 month follow-up. The reported power is based on number of subjects with complete data, and hence is a conservative estimate of the actual power of our design, since the proposed GLMM framework utilizes all observed data collected from all subjects. In addition, the reported power analysis is based on a correlation of 0.5 between measurements obtained at different time points. Selection of the covariance structures within the GLMM model will be based on likelihood ratio test and/or AIC (Akaike Information Criterion). If we find either significant interactions or main effects, follow-up contrasts will be used to determine at which time points there has been significant change and/or differences in treatment effects relative to baseline.

For Aim 2 of detecting group differences in imaging biomarkers, our design with complete data on 55 subjects within each arm at the end of treatment will have 80% power at significance level $\alpha=0.05$ for detecting a group difference between any two arms of $d = 0.53$ SDs. Our preliminary studies reported in Section 1.1.2 for antidepressant treatment response, found effect sizes of $d = 0.57$ for changes in BOLD response in bilateral occipital cortex and right VLPFC (faces affective reactivity task), in BOLD response in left DLPFC, premotor and bilateral posterior parietal regions (N-Back task) between baseline and end of treatment at 16 weeks. If TCC changes in brain function resemble those induced by psychopharmacological agents, our design will have enough power to detect group differences in imaging biomarkers.

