Subjects: We will recruit 220 older depressed adults aged 60 years old or older, all of whom will have a range of depressive symptoms, meet criteria for an episode of major depression, and will be stable on anti-depressant treatment for at least 4 months. Subjects will be recruited, assessed and randomized according to the scientific protocol and the consent procedures approved by the UCLA Institutional Review Board and the Office of Protection of Research Subjects, as well as the analogous units at participating institutions. We anticipate a maximum of 10% dropout in the first 12 weeks; hence, we will have **99 completers per group at 12 weeks**; and an additional 20% dropout at the end of the follow-up period of 12 months (or 24 months if 12 months have passed) (**88 completers per group**).

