4.3 Study Enrollment Procedures

Recruitment of Subjects. Subjects will be recruited, assessed and randomized according to the scientific protocol and the consent procedures approved by the UCLA Institutional Review Board and the Office of Protection of Research Subjects, as well as the analogous units at participating institutions (e.g., Motion Picture and Television Fund). We project a recruitment period of 4.4 years to achieve a study group of **220 subjects**. With the anticipated average of about 4 subjects/month. The incentive to participate appears sufficient since the proposed project offers free TCC and HEW classes to every enrolled patient. In addition, two additional avenues are being developed, such as collaboration with the LA County Department of Mental Health.

We project our minority recruitment at 30%. If the rate of recruitment is not sufficient through the UCLA clinical and research services, advertising in local newspapers will be used. Recruitment through local support groups for depressed patients will also be attempted. [name] also has links to the local community of care providers for the elderly and to mental health professionals, who could serve as a source of referrals. She serves as a Consultant to the LA County Department of Mental Health Services for older adults, an outreach program which should help recruit minority participants. The anticipated rate of recruitment is 39 subjects in year 1 and 40 in year 5 and **47 subjects per year in years 2-4** to accommodate 12/24-month follow-up, a realistic rate for our study. Data analysis will be performed in year 5. We anticipate the dropout to be about **10% in the first 12 weeks, and additional 20 % at 12/24 months**.

Retention of subjects. We have used successful strategies for retention of elderly subjects with depression. These include an ongoing and continuous process of consent to study procedures, involvement of family members whenever possible, and use of concerned and empathic clinicians and staff. However, it is important to note that our data analytic approach is robust to attrition.

Cohort maintenance. The comprehensive evaluation of subjects prior to randomization and entry into the treatment trial is designed to minimize the risk of attrition. The evaluation of weekly compliance questionnaires will also alert the PI to potential attrition problems.

Table 1. Timeline.

Years of the project	ACTIVITIES

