9.6 Data Analyses

Statistical Analysis Plan.

The study will include 220 subjects assigned to TCC/HEW in a 1:1 ratio, within each treatment arm. Prior to performing the primary analyses, descriptive statistics and graphical summaries will be obtained for the primary outcomes (HAMD-24 (Aim 1), connectivity in DMN in rs-fMRI and BOLD activation during the mood task in the anterior cingulate (Aim 2)) to check for outliers and violations of model assumptions and to assess the need for transformations or non-parametric methods. We will also plot each of the primary measures as a function of time to examine the form of the longitudinal trajectories. (HAMD-24 scores will be recorded every 2 weeks throughout the intervention.) Longitudinal analysis proposed will rely on generalized linear mixed models (GLMMs). GLMMs properly account for correlations induced by repeated measurements within subjects, allow for both fixed and time-varying covariates and automatically handle missing data, producing unbiased estimates as long as observations are missing at random. This allows the use of all available data from all subjects, thereby minimizing the effects of loss to follow-up. To make the most efficient use of our data we will fit a single model using all time points for each outcome. Our specific aims and hypotheses correspond to specific contrasts within those models. Demographic variables (e.g., age, gender, etc.) and variables characterizing the course of depressive symptoms (e.g., age of onset, chronicity, number of episodes, length of the current episode, etc.) will be compared by treatment group and examined in relation to outcome variables; this would define one possible set of appropriate covariates, if needed.

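### Follow-up dropout is stated two incompatible ways (88 versus 77–79 completers per arm), and the single d = 0.36 for months 6 and 12 names neither the visits nor the contrast behind it

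*Combined protocol and SAP*

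**What the plan says.** Section 9.6 fixes the size and allocation: "The study will include 220 subjects assigned to TCC/HEW in a 1:1 ratio", so 110 per arm.

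The loss to follow-up is described in three places:

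- **Section 9.2** assumes that "dropout will be at 10% and 20% at the end of 12 week treatment phase and 6 and 12 month follow-up, respectively". It then powers week 12 on 99 per arm and the later follow-up on "complete data on 88 subjects within each arm (20% dropout".
- **Sample Size and Population** (under Design and outcomes) gives 10% loss and 99 completers at week 12, followed by "an additional 20% dropout at the end of the follow-up period of 12 months", and prints "88 completers per group" next to it.
- **Section 4.3** anticipates dropout of "10% in the first 12 weeks, and additional 20 % at 12/24 months".

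On effect size, section 9.2 gives a detectable difference of 0.32 SD at week 12 from seven visits (baseline to week 12). It then supposes that the treatment effect keeps growing linearly and gives one figure, d = 0.36, for 6 and 12 months. The correlation between visits is 0.5. The follow-up visits in the model and the contrast tested are not named.

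**The concern.** The stated 80% power at follow-up is tied to a completer count, and that count does not follow from the dropout as two of the three places describe it. A loss of 20% on top of the first 10% cannot leave 88 of 110.

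The second difficulty is the single effect size. If the arms start level and the difference grows in a straight line, the month-6 difference is about half the month-12 difference. One d for both visits then needs an explanation that the plan does not give.

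Hypothesis 1 in section 1.1 claims benefit at 6 and 12 months as well as at 12 weeks. A reader who wants to know what the trial can show about maintenance has only this power statement to go on.

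**Working it through.** **Inputs.** 110 per arm (section 9.6). Alpha 0.05, power 80%, correlation 0.5, visits at weeks 0, 2, 4, 6, 8, 10 and 12 (section 9.2). Assumptions, because the plan is silent: two-sided test, equal correlation between all pairs of visits, normal approximation (z sum = 1.960 + 0.842 = 2.802), months 6 and 12 at weeks 26 and 52.

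**Step 1: completers per arm.**

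| Reading | Arithmetic | Completers |
|---|---|---|
| 10% at week 12 | 110 x 0.90 | 99 |
| 20% in total | 110 x 0.80 | 88 |
| Further 20% of week-12 completers | 110 x 0.90 x 0.80 | 79.2, so 79 |
| Further 20% of those randomized | 110 x 0.70 | 77 |

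Going from 99 to 88 is a further loss of 11 of 99 (11.1%), or 10 points of those randomized. No reading of a further 20% gives 88.

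**Step 2: reproduce the plan's week-12 figure.** For a test of group by linear time, the detectable difference at the last visit is

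d = t_last x 2.802 x sqrt[(2/n)(1 − 0.5)/SS],

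where SS is the sum of squared deviations of the visit times from their mean. For weeks 0 to 12, SS = 112. With n = 99, d = 12 x 2.802 x sqrt[1/(99 x 112)] = 0.319, against the stated 0.32.

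**Step 3: reproduce 0.36.** Add week 26 to the acute visits: SS = 462. With n = 88, d = 26 x 2.802 x sqrt[1/(88 x 462)] = 0.361. Power at 0.36 is 79.7%. The stated figure is recovered.

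**Step 4: change only n in that model.**

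| n per arm | Detectable d at month 6 | Power at d = 0.36 |
|---|---|---|
| 88 | 0.361 | 79.7% |
| 79 | 0.381 | 75.3% |
| 77 | 0.386 | 74.3% |

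**Step 5: add month 12.** With weeks 26 and 52 both included, SS = 2144. With n = 88, d = 52 x 2.802 x sqrt[1/(88 x 2144)] = 0.335 at month 12. The same line implies 0.335 x 26/52 = 0.168 at month 6. Using weeks 24 and 48 instead gives 0.360 in step 3 and 0.338 at month 12 here, so the choice of week hardly matters.

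**Step 6: how far the visit set matters.** Appendix A also schedules the HAMD at months 4 and 5. Including them at n = 88 gives 0.301 at month 6 (month 12 left out) or 0.330 at month 12. A baseline-adjusted contrast at a single visit gives 2.802 x sqrt[2(1 − 0.25)/88] = 0.366 at either visit, without using linear growth.

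**Step 7: who attends month 12.** Section 6 says that only MRI participants complete the Month 12/24 visit, and that 55 per arm are scanned. On that reading month 12 has 55 x 0.80 = 44 per arm, or about 39 (55 x 0.9 x 0.8 = 39.6; 55 x 0.7 = 38.5). Section 9.5 schedules the 12-month outcomes without that limit.

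**The case against.** **A reader might infer that 88 is a mistake.** The documents do not establish that. Section 9.2 is consistent within itself: 10% and 20%, both taken from 110, give 99 and 88. The population paragraph prints the same 88. The simplest explanation may be a stray *additional* in two places. What stands is that the three statements cannot all be kept.

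**A reader might infer that 0.36 is impossible at both visits.** That holds only for a single fitted slope. Read as a detectable difference at each visit separately, about 0.366 could serve either one, and section 9.2 does foresee follow-up contrasts by time point. Slope models that force no baseline difference also come close: 0.362 for weeks 0, 12 and 26, and 0.356 when week 52 is added. But the single-visit contrast does not use the linear growth on which section 9.2 conditions its figure, and the constrained slope model gives 0.282 at week 12, not 0.32. The phrase about 6 and 12 months may also denote one follow-up phase, since section 9.2 gives it a single dropout rate. So the figure is unexplained rather than impossible.

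**A reader might infer that the maintenance analysis is underpowered.** The fall to 74–75% belongs to the visit set that reproduces 0.36. With month 12 included, power for 0.36 at month 12 is 85.2% at 88 per arm, 81.3% at 79 and 80.3% at 77. Section 9.2 also notes that the mixed model uses all observed data, so complete-case counts understate the information available. Both points stand, and they limit the consequence. They do not remove the need for a stated count that matches the stated dropout.

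**Conclusion.** The follow-up dropout is stated incompatibly: 20% in total in section 9.2 (88 per arm), against 10% and then a further 20% in the population paragraph and section 4.3 (79 or 77). If the second is meant, the detectable difference in the model that matches the plan's figures moves from 0.36 to 0.38–0.39 SD, and power at 0.36 drops by about 4 to 5 points. If the first is meant, 88 and 0.36 are untouched and only the wording is wrong.

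The single d = 0.36 is the month-6 value in the slope model that reproduces 0.32 at week 12. That model does not give 0.36 at month 12. Other contrasts could support a shared value, so the fault is that the visits and contrast are not named.

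These sizes rest on a two-sided test, equal correlation of 0.5 and the visit weeks above. Treatment maintenance is a secondary analysis under section 9.6. The 12-week primary power (99 per arm, 0.32) reproduces and is not affected. The point is worth correcting but modest.

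**What to change.** 1. Choose one dropout assumption and use it in the Sample Size and Population paragraph, section 4.3 and section 9.2. If 20% in total is meant, delete *additional* in the first two and keep 88. If a further 20% is meant, say whether it is taken from week-12 completers (79) or from those randomized (77), and restate the detectable difference (0.381 or 0.386 for the acute visits plus month 6).
2. In section 9.2, name the visits in the model and the contrast behind the follow-up figure, and say whether it uses linear growth.
3. Give n and d separately for month 6 and month 12. Reconcile the month-12 n with section 6, which limits that visit to MRI participants (55 per arm before dropout), and with section 9.5, which does not. Restating month 12 at 77–79 without this step would leave a conflict.

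The cost is a few restated sentences and one recalculation. No more patients are needed, and the primary analysis does not change.

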6. STUDY PROCEDURES

All study assessments will be conducted in a private examination room at either at UCLA Semel Institute or the UCLA Motion Picture Television Fund Campus.

Screening Procedures (Screening / Visits 1a-c): The informed consent form will be reviewed with the participant during the first in-person visit. There will be general medical and psychiatric history taken, vital signs (blood pressure, pulse) (5 minutes duration), and an ECG (electrocardiogram) will be performed (25 minutes). The questionnaires and screening procedures are performed to determine eligibility. The initial visit will last approximately 2 hours.

Clinical Assessments will be performed in 2-3 visits due to participant's burden: (Tables 1;3). Diagnosis. The Structured Clinical Interview DSM-IVTR-5 (SCID)¹²¹ will be used to make a diagnosis of major depression or other mood disorders or rule out other diagnoses (e.g., psychosis and dementia) at screening. Inter-rater reliability for all instruments will be established at the beginning of the trial across both sites and all staff members on the first 5 recruited patients, it will be rechecked routinely twice a year for consistency throughout the study. Master level research associates supervised by the PI will be trained to reliability for the diagnostic interview (SCID) and other assessments. The current inter-rater correlation coefficient (ICC) for SCID ratings among SCID interviewers is ≥ 0.9 . A second level of reliability check is afforded by a bi-weekly diagnostic consensus conference during which diagnosis is also confirmed.

Blood Samples. During screening procedures between 1st in-person visit and visit 2, blood will be drawn by needlestick for routine laboratory testing and genetic analysis (15 minutes). The blood samples will be processed at the UCLA Clinical and Translational Research Center (CTRC). Approximately 8 tablespoons of blood will be drawn. This visit can be combined with either the visits for MRI or Cognitive testing visit.

Screening diagnostic / Neuropsychological Evaluation Visit (Visit 2):

[name] or a designated member from the study staff will conduct a neuropsychiatric evaluation using cognitive assessments during Visit 2 that takes about 2-3 hours.

Visit 3. Magnetic Resonance Imaging (MRI) Scan. One MRI brain scan will be performed. The scan will occur at the UCLA Brain Mapping Center. MRI Safety metal screening will be performed. Only 55 pts/arm will undergo the fMRI procedure.

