MRI Imaging Biomarkers: Imaging data will be acquired from 110 subjects (55 per group) at baseline, at 12-weeks post-randomization (or for early termination), and at 12-months post-randomization on a Siemens Prisma system using a 32-channel head coil. Each scanning session will last 60 minutes and include 1) a T1-weighted multi-echo MPRAGE (MEMPR) sequence with real time motion tracking and correction for the examination of brain structure; 2) a bandwidth matched T2-space sequence for detection and quantification of WMHs and CSF; and 3) three separate BOLD EPI sequences for the acquisition of rs- and task-related fMRI data used for the examination of emotional and working memory processing and functional connectivity. In addition, a 3-plane localizer and a non-BOLD EPI sequence co-planar to the fMRI data for cross-modal image registration will be acquired. The morphometry sequences are optimized for determining brain tissue contrast with reduced distortion.¹¹³

Table 5. fMRI sequences

3D T1 MEMPAGE	TEs/TR= 1.74, 3.6, 5.46, 7.32/2530 ms, TI=1260 ms, FA=7, FOV=256 mm, matrix=256x192, voxel size=1 mm ³ , run time: 8:14 min.
3D T2 SPACE	TE/TR= 425/3200 ms, FA='T2 var', FOV=256 mm, matrix=256x192, voxel size=1 mm ³ , ETL=769, 2xGRAPPA, run time: 4:43 min.
fMRI (emotion and working memory)	TE/TR=25/2500 ms, FA=80°, matrix 64x64, FOV=20 cm, 34 axial slices, slice thickness 3 mm, .75-mm gap, run time: ~6 min each.
Resting state fMRI	TE/TR=30/2000 ms, FA=80°, matrix 64x64, FOV=20 cm, 34 axial slices, slice thickness 3 mm, .75-mm gap, run time: 8 min.

Functional Imaging: To address our hypotheses that TCC versus HEW will result in greater activation in right VLPFC and the amygdala during emotional processing (Hypothesis 2a) and greater working memory-related activation in the DLPFC and other network regions (Hypothesis 2b) we will employ two widely-validated brain activation tasks that probe emotional processing and working memory function (see preliminary studies). Similarly, analysis of rs-fMRI data will

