Aim 2. Hypothesis 2a, b: Primary analysis: Similar to Aim 1, the primary outcomes of DMN connectivity in rs-fMRI and BOLD activation during the mood task in the anterior cingulate will be modeled with a GLMM model with treatment group and time as main effects, along with their two-way interaction. Significant interactions would suggest differential trajectories over time for activation and connectivity outcomes in the two treatment groups. Primary analysis will assess treatment effects at 12 weeks in the primary outcomes. Sensitivity to missing data will be studied as explained in detail in Aim 1. The outcomes of DMN connectivity in rs-fMRI and BOLD activation will be treated as co-primary endpoints and further we will carefully examine the effect size of each co-primary endpoint to ensure clinically meaningful treatment effect.

Secondary analysis: Secondary measures for Aim 2 will be BOLD activation during the cognitive task in hippocampus. Secondary analysis will include assessment of treatment maintenance effects on the primary and secondary outcomes and of treatment effects during treatment in the secondary outcome of BOLD activation during the cognitive task in hippocampus.

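### Aim 2's 80% power counts all 55 scanned per arm as completers, without the plan's own 10% dropout, and covers one test although two co-primary imaging endpoints are named with no success rule

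*Combined protocol and SAP*

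**What the plan says.** **Power.** In section 9.2 the Aim 2 statement is that "our design with complete data on 55 subjects within each arm at the end of treatment will have 80% power", at α = 0.05, to detect d = 0.53 SDs. It supports this with preliminary effect sizes of 0.57.

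**Number scanned.** Section 6, Visit 3: "Only 55 pts/arm will undergo the fMRI procedure". Section 6.2.1 agrees: "Imaging data will be acquired from 110 subjects (55 per group) at baseline, at 12-weeks post-randomization (or for early termination". So 55 per arm is the intake to imaging at baseline, not a number left after losses.

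**Dropout.** The Sample Size and Population paragraph (ahead of section 4) says: "We anticipate a maximum of 10% dropout in the first 12 weeks". Section 9.2 repeats the 10% and uses it for Aim 1, where power is computed "with complete data on 99 subjects within each arm (10% dropout").

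**Endpoints.** The opening of section 9.6 lists among the primary outcomes "connectivity in DMN in rs-fMRI and BOLD activation during the mood task in the anterior cingulate (Aim 2"). The Aim 2 paragraph puts their primary analysis at 12 weeks and adds: "The outcomes of DMN connectivity in rs-fMRI and BOLD activation will be treated as co-primary endpoints". The same sentence goes on: "we will carefully examine the effect size of each co-primary endpoint to ensure clinically meaningful treatment effect". No section says whether both or either must be significant, splits alpha, or gives power for the pair.

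**The concern.** Two consecutive paragraphs of section 9.2 treat the same 12-week time point differently. Aim 1 is powered on enrolled subjects less 10%; Aim 2 is powered on every subject scanned. Under the plan's own dropout assumption, the stated 80% for imaging is not delivered.

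The second gap is larger. The power statement describes one test, but the analysis section names two co-primary endpoints. If one is significant and the other is not, the plan does not say whether Aim 2 has succeeded, so that result could be called either way once the data are seen. The power and the alpha needed also depend on the choice. Requiring both keeps each test at 0.05 but lowers joint power. Accepting either raises the chance of a finding but needs alpha control.

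**Working it through.** **Inputs from the documents.** 55 scanned per arm (sections 6 and 6.2.1); 1:1 allocation (section 9.6); α = 0.05, power 80%, d = 0.53, cited d = 0.57, 10% dropout at 12 weeks (section 9.2); two co-primary endpoints (section 9.6). Sidedness is not stated. Two-sided is used because it reproduces the plan's figure; one-sided gives 87% and does not.

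**Step 1: reproduce the stated figure.** For two means, power ≈ Φ(d·√(n/2) − 1.96).
- n = 55, d = 0.53: 0.53 × √27.5 = 2.779; Φ(0.819) = 79.4%. With the t distribution, 78.7%.
- Detectable d at 80% = (1.960 + 0.842) × √(2/55) = 0.534 (t: 0.539).

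The plan's figure is right for its input: one unadjusted two-sided test on all 55 per arm. A change score with the plan's within-subject correlation of 0.5 has the same variance, since 2(1 − 0.5) = 1.

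**Step 2: deduct 10%.** 55 × 0.9 = 49.5 per arm.
- Power at d = 0.53: 0.53 × √24.75 = 2.637; Φ(0.677) = 75.1% (t: 74.2%).
- Detectable d at 80%: 2.802 × √(2/49.5) = 0.563 (t: 0.569).

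| Complete per arm | Power at d = 0.53 (t / z) | Detectable d (t / z) |
|---|---|---|
| 55 (every dropout gives a scan that counts) | 78.7% / 79.4% | 0.539 / 0.534 |
| 52 (about half do) | 76.3% / 77.1% | 0.555 / 0.549 |
| 50 | 74.7% / 75.5% | 0.566 / 0.560 |
| 49.5 | 74.2% / 75.1% | 0.569 / 0.563 |
| 49 | 73.8% / 74.6% | 0.572 / 0.566 |

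**Step 3: two endpoints.** Assumptions not in the documents: the same d on both endpoints, test statistics bivariate normal, correlation r from 0 to 0.8. With λ = d·√(n/2):
- Both required, each at 0.05: P(Z₁ > 1.96 and Z₂ > 1.96), each Z having mean λ.
- At least one under Holm: the first step is at 0.025, so 1 − P(Z₁ < 2.241 and Z₂ < 2.241).

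| n per arm, d = 0.53 | r = 0 | r = 0.3 | r = 0.5 | r = 0.8 |
|---|---|---|---|---|
| 49.5, both required | 56.4% | 59.6% | 62.1% | 67.0% |
| 49.5, at least one (Holm) | 88.0% | 83.8% | 80.7% | 74.8% |
| 55, both required | 63.0% | 65.7% | 67.9% | 72.1% |
| 55, at least one (Holm) | 91.3% | 87.5% | 84.7% | 79.3% |

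Check at r = 0 with 49.5 per arm: 0.751² = 0.564.

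So even with no dropout, the both-required figure is below 80% across the assumed range.

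**The case against.** **The dropout loss is small and may be recovered.** This largely stands. It costs 4-5 points of power on a secondary aim, the plan calls 10% a maximum, and section 6.2.1 allows a scan at early termination. But the power statement claims complete data at the end of treatment and does not say that earlier scans count. Section 9.2 calls its power conservative because the mixed model uses all observed data. That helps Aim 1, where fewer are counted than enrolled; for Aim 2 the number counted is already everyone scanned.

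**Power is still about 80% at the cited d = 0.57.** Numerically true for one test: 80.2% (t) at 49.5 per arm. But section 9.2 describes 0.57 as a baseline-to-16-week change under antidepressant treatment, in occipital, VLPFC, DLPFC, premotor and parietal regions. That is neither a TCC-HEW difference nor a result for DMN connectivity or the anterior cingulate, and the plan itself makes the transfer conditional. It does not serve as a benchmark.

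**Baseline adjustment would gain power.** It could: with correlation 0.5 the residual SD shrinks by √0.75, and one test at 49.5 per arm has about 86% power. That is not the basis of the stated figure, which reproduces only without it.

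**Co-primary usually means both.** A fair reading, and the clause on each endpoint's effect size fits it. But section 1.2 lists the two as separate hypotheses, 2a and 2b, and the plan never defines success for Aim 2. Examining effect sizes is not a decision rule.

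**Stronger readings that the documents do not support.** A reader might infer a calculation error; there is none. A reader might take 49-50 per arm as a floor, but 10% is trial dropout, not loss of usable scans, and section 5.5 lets MRI move from its planned date. A reader might infer an inflated false-positive rate, but the plan does not say that either endpoint suffices at an unadjusted 0.05.

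**Conclusion.** The point holds as one of assumptions and multiplicity. Under the plan's own 10% dropout, Aim 2 has about 74-75% power at d = 0.53 for a single two-sided test, and 80% power needs d of about 0.57. Counting early-termination scans would restore up to 79%; unusable or missed scans would push the figure down by an amount that the documents do not allow one to estimate.

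The missing success rule matters more. At d = 0.53 with 49.5 per arm, power is 56-67% if both endpoints are required and 75-88% for at least one under Holm. These ranges illustrate how far the answer depends on the rule. They are not the trial's stated position, because the equal effect sizes, the 0-0.8 correlation and Holm itself are assumptions made here.

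Confidence is high on the omitted dropout and the absent rule, and lower on the two-endpoint ranges. Aim 2 is a secondary objective, so the change is advisable rather than critical.

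**What to change.** 1. **Section 9.2, Aim 2.** Restate power for 49-50 completers per arm: detectable d about 0.57 at 80%, or about 74-75% power at d = 0.53, for one endpoint. Say whether early-termination scans count as end-of-treatment data. If an allowance for unusable or missed scans is added, label it as an assumption.
2. **Section 9.6, Aim 2.** Before unblinding, state one rule: both endpoints significant at 0.05, or Holm across the two. Give power under that rule, with the assumed effect sizes and correlation shown.
3. **Separate consistency edit.** Section 6.2.1 ties Hypotheses 2a and 2b to VLPFC/amygdala and DLPFC activation, and section 9.5.2 ranks imaging outcomes as secondary or exploratory. Reconcile both with section 1.2 and with section 9.6, where DMN connectivity and anterior cingulate activation are primary for Aim 2.

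The cost is protocol and SAP wording, with no extra scans. The stated power becomes less favourable: joint power below 80% if both are required (under the assumptions above), or a first test at 0.025 under Holm, where the detectable d at 49.5 per arm is about 0.63 (t).
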